8.2.3.3 Medically Attended Adverse Events

An MAAE is defined as an AE that leads to an unscheduled visit to a healthcare practitioner.

8.2.3.4 Reactogenicity Symptoms

On the day of vaccination, participants will remain in clinic (or under observation) for at least 15 minutes to be observed for any immediate hypersensitivity and anaphylaxis reactions. Site specific local and general systemic reactogenicity reactions including start and stop dates will be recorded following vaccination.

Participants will utilize their eDiary to record reactogenicity following vaccination. All participants will be asked to record reactogenicity following vaccination on Day 0 and then daily for an additional 6 days after vaccination. Study site personnel should regularly review the

SARS-CoV-2 rS Vaccines	Study Protocol 2019nCoV-314 Amendme	ent 2 v4.0
Novavax	Confidential	Page 57

eDiary for completeness. Should any reactogenicity event extend beyond 6 days after vaccination, then it will be recorded using the Continuing Solicited AE form and followed to resolution per ICH guidelines for AE capture. Such AEs should be reported and managed as described in Section 8.3. The toxicology grading scale implemented in the eDiary for the study is included in Appendix 2.

8.3 Reporting Adverse Events

All SAEs must be reported according to ICH Good Clinical Practice (GCP) or local regulations, applying the regulation with the stricter requirements. Investigators and other study site personnel must inform appropriate Novavax representatives of any SAE that occurs during the course of the study, from the time of informed consent until the EOS visit, regardless of whether it is judged to be causally related to study vaccine or procedures. Notification must occur within 24 hours of when they become aware of it. AESIs, including PIMMC, myocarditis or pericarditis and complications specific to COVID-19 are to be reported within these timelines on the SAE/AESI Report form. The investigator should make every effort to obtain follow-up information on the outcome until the event is considered resolved, chronic and/or stable.

SAE reports received that may be attributed to both the study vaccine and an approved/authorized vaccine from a different manufacturer will be reported to local regulatory authorities as applicable. SAE reporting forms allow for the notation of other factors that may have impacted the investigator's assessment of causality. Investigators will be instructed to utilize this section of the reporting form to note the impact of an approved/authorized vaccine from a different manufacturer on the event, if applicable. Investigators will be required to report any SAEs in participants who received a different manufacturer's approved/authorized vaccine to local health care and/or regulatory authorities as per the local regulatory guidelines.

If a non-serious AE becomes serious, this and other relevant follow-up information must also be provided to Novavax Global Vaccine Safety within 24 hours as described above. The date when the AE becomes serious should be notated in the eCRF or on the SAE form.

All SAEs and AESI will also be recorded in the eCRF. The investigator is responsible for informing the Independent Ethics Committee (IEC)/IRB of the SAE as per local requirements. Paper SAE forms should be completed at the study site and emailed within 24 hours of study site awareness of the event to the Novavax Global Vaccine Safety mailbox:

The report form should be attached to the email; a notification email of the event describing it in the email text is not sufficient. There may be situations when an SAE has occurred, and the investigator has minimal information to include in the initial SAE report. However, it is very important that the investigator always makes an assessment of causality for every event prior to transmission of the SAE report form.

Minimum criteria for a reportable event are:

- Identifiable patient (participant number)
- A suspect product (ie, study vaccine)
- An identifiable reporting source (investigator/study site identification), and
- An event or outcome that can be identified as serious.

Follow-up information on SAEs must also be reported by the investigator within the same time frames.

8.3.1 Safety Reporting to Health Authorities, Independent Ethics Committees/Institutional Review Boards, and Investigators

Novavax or its designee will be responsible for notifications of SAEs and other qualifying events that are considered to be unexpected and related to study vaccine as expedited (eg, 7- or 15-Day reports to the relevant regulatory authorities and to participating investigators. In addition, Novavax or its designee will follow all applicable local and national regulatory requirements regarding safety reporting. Each investigator must comply with any applicable study local and national regulatory requirements related to the reporting of SAEs to the IRB/IECs responsible for reviewing the trial at their site, as well as the regulatory authority(ies) (where applicable).

Timelines and responsibilities (Novavax and its designee) for expedited and periodic safety reporting to the Health Authorities, Independent Ethics Committees/ Institutional Review Boards, and Investigators are provided in the Safety Management Plan as agreed by the Syneos designee and Novavax.

8.3.2 24/7 Medical Emergency Coverage for Urgent Protocol-related Medical Questions

In a study-related health emergency, when assigned medical monitors for a study cannot be reached by a caller, for discussion of urgent medical related questions an on-call physician can be reached 24 hours 7 days a week (24/7) via Syneos Call Center:

• Telephone:

8.4 Pregnancy

Pregnancy is not considered an AE unless there is a suspicion that an investigational vaccine may have interfered with the effectiveness of a contraceptive medication. Any pregnancy that occurs during study participation must be reported using the Pregnancy Assessment form. To ensure participant safety, each pregnancy must be reported to Novavax Global Vaccine Safety within 24 hours of learning of its occurrence. If pregnancy occurs, further vaccination will be discontinued. Pregnancy must be followed up to determine outcome (including spontaneous miscarriage, elective termination, normal birth, or congenital abnormality) and the status of both mother and child, even if the participant was discontinued from the study. Pregnancy

complications and elective terminations for medical reasons must be reported as an AE or SAE. Spontaneous miscarriages must be reported as an SAE.

Any pregnancy brought to the investigator's attention before the study is completed should be reported to Novavax Global Vaccine Safety using the Pregnancy Assessment form provided to sites.

Any pregnancy brought to the investigator's attention after the participant has completed the study but occurring while the participant was in the study must be promptly reported to:

Novavax Global Vaccine Safety:

8.5 Overdose or Misuse

A drug overdose is defined as the accidental or intentional use of an IP or an administration error in an amount that is higher than is normally used. Every overdose must be reported to Novavax Global Vaccine Safety within 24 hours of awareness, using the details provided in Section 8.3 if the overdose was associated with an SAE. Other overdoses and those associated with non-serious AEs should be reported in the AE eCRF. Only overdoses associated with a clinical SAE need to be reported as an SAE. The quantity and details regarding the excess dose should be documented in the eCRF.

Overdose in this study is specifically defined as any dose greater than the intended protocol dose (Section 7). In case of overdose, it is recommended that the participant be monitored for any signs or symptoms of adverse reactions or effects and appropriate symptomatic treatment be administered immediately. Note that administration of the "wrong" vaccine is a protocol deviation, but not, in the absence of associated AE, an SAE.

9 ANALYSIS

9.1 Sample Size Calculations

The sample size for this study is based on clinical and practical considerations and not on a formal statistical power calculation. The sample size is considered sufficient to evaluate the objectives of the study. With 200 participants in each treatment group, there is a greater than 99.9% probability to observe at least 1 subject with an AE if the true incidence of the AE is 5% and an 86.6% probability if the true incidence of the AE is 1%.

9.2 Analysis Sets

The following analysis sets are identified for analysis.

9.2.1 All Randomized Participants Analysis Set

The All Randomized Participants Analysis Set will include all participants who are randomized/enrolled, regardless of whether they actually received any study vaccine. The All Randomized Participants Analysis Set will be used for participant disposition summaries and will be analyzed according to the treatment as randomized/enrolled.

9.2.2 Full Analysis Set

The Full Analysis Set (FAS) will include all participants who are randomized/enrolled and received at least 1 dose of study vaccine, regardless of protocol violations or missing data. The FAS may be the secondary analysis set used for any immunogenicity analyses and will be analyzed according to the treatment as randomized.

9.2.3 Safety Analysis Set

The Safety Analysis Set will include all participants who provide consent, are randomized, and receive at least 1 dose of study vaccine. Participants in the Safety Analysis Set will be analyzed as actually treated.

9.2.4 Per-Protocol Analysis Set

The Per-Protocol (PP) Analysis Set will be determined for each strain, serology assay and study visit. The PP Analysis set will include all participants who receive the full prescribed regimen of the study vaccine up to the visit according to protocol, have serology results for baseline and the time point analyzed, are PCR negative at baseline for SARS-CoV-2, and have no major protocol violations or an event (eg, COVID-19 infection) that are considered clinically relevant to impact immunogenicity response as determined prior to database lock.

Within the PP Analysis Set there are 3 subsets defined:

9.2.4.1 Anti-S Protein IgG Serology Subset

All participants in the PP Analysis Set who are tested for anti-S protein IgG serology using ELISA at each timepoint will be included in this subset.

9.2.4.2 Neutralization Assay Subset

All participants in the PP Analysis Set who are tested using the neutralization assay at each timepoint will be included in this subset.

9.2.4.3 hACE2 Receptor-Binding Inhibition Assay Subset

All participants in the PP Analysis Set who are tested for hACE2 receptor-binding inhibition titers at each timepoint will be included in this subset.

9.2.4.4 Mucosal hACE2 Receptor Binding Inhibition Assay Subset

All participants in the PP Analysis Set who are tested for mucosal IgA-mediated hACE2 receptor binding inhibition titers at each time point will be included in this subset.

9.3 Analyses to be Performed

9.3.1 Safety Analysis

All safety analyses will be descriptive and conducted using the Safety Analysis Set. Listings will be provided for all safety parameters collected.

9.3.1.1 Solicited Adverse Events

The number and percentage of participants with solicited injection site and systemic AEs through 7 days after vaccination will be summarized overall and by vaccine group and by the worst maximum toxicity grade over 7 days. The durations of solicited local and systemic AEs after vaccination within the 7 Day diary period and entire safety follow-up period will also be summarized by vaccine group.

9.3.1.2 Unsolicited Adverse Events

Unsolicited AEs will be coded by system organ class (SOC) and preferred term (PT) using Medical Dictionary for Regulatory Activities (MedDRA).

Unsolicited AEs will be summarized according to the periods described in Section 8.2.2 both overall and by vaccine group and by SOC/PT, as well as by severity and relationship to the study vaccine to present the number and percentage with corresponding exact 95% CIs using the Clopper-Pearson method. For multiple occurrences of an adverse event in the same participant, a participant will be counted only once, using the most severe or most related occurrence for the summarization by severity or relationship to the study vaccine, respectively.

All MAAEs (only related MAAEs beyond 28 days following vaccination), AESIs (predefined list), and SAEs throughout the study (up to the time of pre-planned analyses) will be summarized overall and by vaccine group as well as by severity.

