3 OBJECTIVES AND ENDPOINTS

The primary objectives in this study are to assess the overall safety of 1 heterologous booster dose of NVX-CoV2601 and the bivalent vaccine (NVX-CoV2373 + NVX-CoV2601) and to describe the NAb responses induced against the Omicron XBB.1.5 strain. An overview of the study objectives and endpoints is provided in Table 2.

Tier	Objectives	Endpoints
Primary Safety Objective and Endpoints	To assess the overall safety of 1 heterologous booster dose of NVX-CoV2601 and the bivalent vaccine (NVX-CoV2373 + NVX-CoV2601).	 Incidence, duration, and severity of solicited local and systemic AEs for 7 days following vaccination. Incidence, severity, and relationship of unsolicited AEs through 28 days after vaccination Incidence and severity of MAAEs attributed to study vaccine, AESIs (predefined list including PIMMCs, myocarditis and/or pericarditis, and complications specific to COVID-19), and SAEs through day 180 or EOS.

 Table 2:
 Study 2019nCoV-314 Objectives and Endpoints

Tier	Objectives	Endpoints
Primary Immunogenicity Objective and Endpoints	To describe the NAb response induced by NVX-CoV2601 and the bivalent vaccine (NVX-CoV2373 + NVX-CoV2601) against the Omicron XBB.1.5 strain.	 NAb GMTs to the Omicron XBB.1.5 strain, assessed at Day 28 following initial study vaccination. NAb geometric mean fold rise (GMFR) at Day 28 from baseline (Day 0).
Secondary Objectives	To describe the NAb response induced by NVX-CoV2601 and the bivalent vaccine (NVX-CoV2373 + NVX-CoV2601) against the Omicron XBB.1.5 strain over time.	 NAb GMTs to the Omicron XBB.1.5 strain at relevant time points (Days 0, 90, and 180). NAb GMFR at relevant time points (Days 90 and 180) from baseline (Day 0)
	To describe immunoglobulin G (IgG) antibody levels induced by NVX-CoV2601 and the bivalent vaccine (NVX-CoV2373 + NVX-CoV2601) against the Omicron XBB.1.5 strain over time.	• IgG GMEUs to the Omicron XBB.1.5 S protein at relevant time points (Days 0, 90, and 180). Derived/calculated endpoints based on these data will include GMFR.
Exploratory	To describe the NAb and IgG antibody responses induced by NVX-CoV2601 and the bivalent vaccine (NVX-CoV2373 + NVX-CoV2601) against the ancestral (Wuhan) strain over time.	 NAb titers and IgG GMEUs to the ancestral (Wuhan) strain at relevant time points (Days 0, 90, and 180). Derived/calculated endpoints based on these data will include GMFR.

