8.2 Documenting Adverse Events

At every study visit, participants will be asked to report any medically related changes in their well-being. They will also be asked if they have been hospitalized, had any accidents, used any new medications, or changed concomitant medication regimens (both prescription and OTC medications).

In addition to participant observations, AEs will be documented from any data collected on the AE page of the eCRF or other documents that are relevant to participant safety.

Care will be taken not to introduce bias when detecting AEs, MAAEs, and SAEs. Open ended and non-leading verbal questioning of the participant is the preferred method to enquire about AE occurrences. AESIs will be inquired about according to the specific diseases listed in Appendix 1.

When an AE/SAE occurs, it is the responsibility of the investigator to review all available documentation (eg, hospital progress notes, laboratory reports, and diagnostics reports) related to the event. The investigator will then record all relevant AE/SAE information in the eCRF.

It is not acceptable for the investigator to send photocopies of the participant's medical records in lieu of completion of the AE/SAE eCRF page. There may be instances when copies of medical records for certain cases are requested. In this case, all participant identifiers, with the exception of the participant number, will be redacted on the copies of the medical records before submission. The investigator will attempt to establish a diagnosis of the event based on signs, symptoms, and/or other clinical information. Whenever possible, the diagnosis (not the individual signs/symptoms) will be documented as the AE/SAE. The following variables will be recorded for each AE: verbatim/AE description and date for AE start and stop, severity, seriousness, causality, any other action taken, and the outcome. A new AE must be recorded if the severity of the AE changes.

Should an SAE have an outcome of death, the report should contain a comment regarding the co-involvement of progression of disease, if appropriate, and should assign main and contributory causes of death.

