8.2.2 Time Frame for Collection

All AEs captured following the procedures listed in the SOE (Section 1.1) will be recorded on the AE page of the eCRF.

Medical occurrences that begin prior to study vaccination will be recorded on the Medical History/Current Medical Conditions section of the eCRF and not in the AE section.

All unsolicited AEs of any severity will be collected from the time of study vaccination through 28 days after vaccination.

All MAAEs will be collected through 28 days after vaccination and only treatment-related MAAEs will be collected after Day 28 until EOS.

All AESIs will be collected from the time of study vaccination until EOS.

All SAEs will be collected from signing of informed consent until completion of the EOS.

All vaccine administration errors, AEs, SAEs, cases of multisystem inflammatory syndrome, and all cases of COVID19 following vaccination must be reported per applicable local regulatory reporting guidance for safety events that occur in participants during the study if they meet the regulatory reporting criteria.

At any time after completion of the EOS visit, if an investigator learns of an SAE that could reasonably be considered related to study vaccine, they should promptly notify the Sponsor.

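### Section 9.3.1.2 specifies the MAAE summary by the collection rule, not by the primary safety endpoint of vaccine-related MAAEs through Day 180/EOS

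*Protocol*

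**What the plan says.** **Endpoint.** Protocol Section 3, Table 2, lists as one primary safety endpoint: "Incidence and severity of MAAEs attributed to study vaccine, AESIs (predefined list including PIMMCs". The same bullet ends with "complications specific to COVID-19), and SAEs through day 180 or EOS", which gives the window.

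**Collection.** Section 8.2.2 states: "All MAAEs will be collected through 28 days after vaccination and only treatment-related MAAEs will be collected after Day 28 until EOS".

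**Analysis.** The last paragraph of Section 9.3.1.2 covers "All MAAEs (only related MAAEs beyond 28 days following vaccination), AESIs (predefined list), and SAEs throughout the study", up to the time of each planned analysis. These "will be summarized overall and by vaccine group as well as by severity".

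**Neighbouring text.** The paragraph before it, on unsolicited AEs, refers to the periods in Section 8.2.2 and asks for summaries by SOC and PT, "as well as by severity and relationship to the study vaccine to present the number and percentage", with exact Clopper-Pearson intervals. Section 8.2 requires several items to be recorded for each AE, among them "start and stop, severity, seriousness, causality, any other action taken, and the outcome".

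**The concern.** The endpoint counts events by cause: related MAAEs over one window of about six months. The analysis sentence counts them by what the database will hold: every MAAE to Day 28, then related ones only. Its event definition changes at Day 28. Over the whole study it is therefore neither related MAAEs nor all-cause MAAEs.

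This matters because Section 4.1.3 says that sample size and duration were chosen to favour safety data, and this is one of the primary safety endpoints. Section 8.2.3.3 defines an MAAE broadly, as any AE that prompts an unplanned visit to a practitioner, so unrelated illness and injury in the first 28 days would qualify. An analyst who follows Section 9.3.1.2 to the letter would produce a figure that is not the one named in Table 2, and could report it under that endpoint's label.

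The row could also change meaning between reports. Section 9.5 expects the interim extract to hold safety data through Day 28, so MAAEs there would be essentially all-cause. At the final analysis the same row would mix two definitions.

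**Working it through.** **1. The plan's nearest figure.** No stated number bears directly on this point. The only related figure is in Section 9.1: with 200 per group, the chance of seeing at least one participant with an AE. The formula is 1 - (1 - p)^200.
- p = 5%: 1 - 0.95^200 = 0.99996 (stated as greater than 99.9%).
- p = 1%: 1 - 0.99^200 = 0.8660 (stated as 86.6%).

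Both reproduce, and neither is affected.

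**2. The texts side by side.**

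| Feature | Endpoint (Table 2) | Collection (8.2.2) | Analysis (9.3.1.2) |
|---|---|---|---|
| Day 0-28 | related only | all causes | all causes |
| Day 29 to EOS | related only | related only | related only |
| Breakdown | severity | not applicable | group and severity, not relationship |

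The analysis column matches the collection column and departs from the endpoint column in the first 28 days.

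**3. Does the preceding paragraph close the gap?** There are three ways to read it.
- *It does not extend to MAAEs as a class.* It concerns unsolicited AEs as a whole by SOC and PT, and the MAAE sentence then sets its own breakdown without relationship. No related-only MAAE summary results.
- *MAAEs inherit only the split by Section 8.2.2 period.* The Day 0-28 summary is still all-cause, so related MAAEs in that period are not isolated.
- *MAAEs inherit both the period and the relationship split.* Related MAAEs would then be visible in each period. Incidence through Day 180 still needs participants counted once across both periods. Severity and relationship are also listed as separate breakdowns, so severity among related MAAEs, which Table 2 asks for, is still not specified.

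**4. Illustration of scale (all rates assumed).** Let u be the risk of an unrelated MAAE by Day 28 and r the risk of a related MAAE by Day 180, taken as independent. If one count were made over the whole study, its proportion would be 1 - (1 - u)(1 - r), against r for the endpoint. With n = 200 and r = 1% (2 participants):

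| u | Mixed proportion | Participants |
|---|---|---|
| 2% | 1 - 0.98 × 0.99 = 3.0% | 6.0 |
| 5% | 1 - 0.95 × 0.99 = 6.0% | 11.9 |
| 10% | 1 - 0.90 × 0.99 = 10.9% | 21.8 |
| 15% | 1 - 0.85 × 0.99 = 15.8% | 31.7 |

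Over r = 0.5% to 2% and u = 2% to 15%, the ratio of mixed count to endpoint count runs from 0.0396/0.02 = 2.0 to 0.1542/0.005 = 30.8.

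**5. Can the endpoint be derived?** Yes. Causality is recorded for every AE (Section 8.2), and related MAAEs are collected from vaccination to EOS (Section 8.2.2).

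**The case against.** The strongest reply is that the parenthesis in Section 9.3.1.2 only reminds the analyst which MAAEs exist in each period, and that MAAEs, as unsolicited AEs, take the period split, the relationship split and the intervals from the paragraph above. A reader might infer that the protocol orders a single pooled Day 0-180 count. It does not expressly do so, and that part of the reply stands. The rest does not remove the point: the MAAE sentence repeats severity but omits relationship, and a split by period alone leaves the first 28 days all-cause.

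A second reply is that table layout belongs in the SAP, which is not at hand. That would answer a complaint about missing detail. Here the protocol does state an MAAE analysis, and it does not match the protocol's own endpoint. The SAP may put this right, and Section 9.7 provides for documenting such a change.

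A third reply is that little hangs on it. Safety analyses are descriptive (Section 9.3.1), so no test or decision rule depends on the rate, and the collection rule is the same in both randomised groups. This stands, and it limits the weight of the point.

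**Conclusion.** The mismatch is real and rests on the text alone: Section 9.3.1.2 does not specify a summary of the Table 2 endpoint for MAAEs. It is a fault in the wording of the analysis, not a gap in the data, and it is worth correcting before the tables are produced.

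Its numerical size is unknown. The ratio of about 2 to 31 depends on assumed rates, on independence and on a single count being made. It shows only that the two quantities could differ a good deal.

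Three stronger readings might be inferred, and the documents do not support them:
- That unrelated visits will dominate the reported figure. No MAAE rates are given.
- That the comparison between groups is biased. The same rule applies to both.
- That the report will show a misleading fall in MAAEs after Day 28. No before-and-after comparison is planned.

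**What to change.** In Section 9.3.1.2, replace the MAAE clause with two summaries, overall and by vaccine group and severity, each with the Clopper-Pearson intervals already named there:

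- (a) related MAAEs from Day 0 to Day 180/EOS, labelled as the primary safety endpoint, with each participant counted once and severity taken from the related events;
- (b) all MAAEs from Day 0 to Day 28, labelled as supportive.

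Add that all-cause and related-only periods are not to be combined in one count. The wording for AESIs and SAEs can stay.

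The cost is one sentence and one extra table. No new data, visits or participants are needed.
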